10.0 ASSESSMENT OF EFFICACY

10.1 Specification of the efficacy parameters.

10.1.1 Primary efficacy variable

The primary outcome measures will be adherence to anti-seizure medications as measured by self-reports and validated by optimal and detectable levels in blood.

10.1.2 Secondary efficacy variable(s)

- (i) Correct intake of drugs and refill rates- measured by checking record logs for participants attending the epilepsy clinics and identified in the surveys in NUHDSS
- (ii) Changes in seizure frequency as assessed by trained clinicians at the epilepsy clinics and identified in the surveys in NUHDSS
- (iii) Changes in stigma scores and quality of life scores assessed using standardized scales
- (iv) Unwanted drug-related adverse events as reported by participants and confirmed using standardized questionnaires.

11.0 EVALUATION OF COST EFFECTIVENESS OF THE INTERVENTION

The impact of measures to address the epilepsy treatment will be used to inform economic modelling that we will undertake to calculate the return on investment from investing in management. A decision analysis model will be constructed by collating data on the resources required for treatment strategies in epilepsy care.

In addition, we shall draw on existing analyses of the costs of epilepsy, to estimate economic benefits from a health and societal perspective of averting epilepsy. The costs of treating epilepsy will be estimated by adapting existing resource use and cost estimates from Ethiopia so that they match the local Kenyan context using the WHO's One Health Tool. Threshold analysis to identify the minimum level of effectiveness and/or costs needed to generate a positive return on investment. Drawing on data on the QoL benefits associated with preventing epilepsy a net monetary benefit approach to determining the economic case for action will also be conducted.

Crucial to the sustainability of the project, although initially tailored to the local context in Kenya, the economic model will be made available in Excel format as a legacy of the proposal. Decision makers in SSA would then be able to look at the potential return on investment in their own contexts. They would be able to vary assumptions on

population reached, effectiveness, coverage, resource requirements and the short and longer-term costs of both treated and untreated epilepsy.

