6.3 Secondary objective(s)

- (i) Using qualitative methods, to describe the perceptions and perspectives of PWE and their caregivers on the use of text and graphic SMS reminders to improve adherence to ASMs among PWE in Kilifi and Nairobi, Kenya
- (ii) To compare the effectiveness of text versus graphic messaging service or both in improving adherence among people with epilepsy in Kilifi and Nairobi, Kenya
- (iii) To identify the factors associated with an improvement in adherence and improved QoL among PWE and reduction in stigma among PWE and their family members.
- (iv) To document the adverse drug reactions (ADRs) including neurologic and psychiatric ADRs related to frequently prescribed ASMs types and, where possible, plasma levels among PWE in Kilifi and Nairobi, Kenya
- (v) To conduct cost-effectiveness analysis of rolling out the interventions among PWE in Kilifi and Nairobi, Kenya

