8.0 DESCRIPTION OF THE INTERVENTION

8.1 Intervention

The intervention will be a short message service (SMS) reminder sent to the mobile phones of participants in the intervention group reminding them to take their anti-seizure medications. This will be a behavioural intervention with no investigational medicinal product. Each SMS (text or graphic or both) adherence message will be 120–140 characters long. To increase the probability that that the PWE or family member will read the messages and support family members with epilepsy, message will be randomly complemented with a quote (up to 60 characters long) and unrelated to epilepsy treatment, but designed to be motivating, entertaining, or merely attention-getting. This motivational element was used with success in the health workers adherence to antimalarial guideline studies. The graphics will be hand drawn by a local illustrator and the accompanying text of no more than 15 characters will be scanned and sent as low-resolution jpeg files, suitable for the MMS format that is compatible with basic phones.

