9.2.2 Eligibility criteria

9.2.2.1 Inclusion criteria

- (i) Children or adults with a diagnosis of epilepsy ascertained by a clinician at the epilepsy clinic
- (ii) Taking anti-seizure medications at the time of the study
- (iii) Living within an area defined as the Kilifi Health Demographic Surveillance System, or the Nairobi Urban Health and Demographic Surveillance System at the time of the study or attending the epilepsy clinic in Kilifi or a KAWE-led clinic in Nairobi
- (iv) Able to give written informed consent or assent in addition to parental consent (if aged between 13 and 17 years old) to participate in the study either by themselves or in the presence of an independent witness

(v) Access to a basic mobile phone in the household

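### The net monetary benefit analysis values preventing epilepsy, a benefit that reminders to people already diagnosed and treated cannot produce; it should value the effects the trial measures

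*Combined protocol and SAP*

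**What the plan says.** Section 11.0 names its benefit in two places. Existing cost analyses will be used "to estimate economic benefits from a health and societal perspective of averting epilepsy". The net-benefit step is described as "Drawing on data on the QoL benefits associated with preventing epilepsy a net monetary benefit approach to determining the economic case for action".

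The same section also opens with a model meant to "calculate the return on investment from investing in management", informed by the impact of measures on treatment. It adds a threshold analysis for the least effectiveness, or the costs, at which the return turns positive. It promises a spreadsheet model whose users can vary "population reached, effectiveness, coverage, resource requirements and the short and longer-term costs of both treated and untreated epilepsy".

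The economic objective, section 6.3 (v), is "To conduct cost-effectiveness analysis of rolling out the interventions among PWE in Kilifi and Nairobi, Kenya". The synopsis (section 1.4) asks for this in each site. Section 9.2.2.1 admits "Children or adults with a diagnosis of epilepsy ascertained by a clinician at the epilepsy clinic" who are also "Taking anti-seizure medications at the time of the study". Section 8.1 describes the intervention as a message "reminding them to take their anti-seizure medications".

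**The concern.** A cost-effectiveness analysis of a reminder should value what the reminder changes. Nobody enrolled can have epilepsy prevented, because a diagnosis is a condition of entry. The value of a case averted is the whole burden of the disease. The value of better adherence is, at most, the part of that burden that treatment removes in people whose adherence improves. Using the first in place of the second pushes the result in the favourable direction.

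Two things raise the stakes. If each unit of effect in the threshold analysis were priced as a case prevented, the minimum effectiveness would be set too low. The spreadsheet model is also meant for decision makers elsewhere in sub-Saharan Africa, so a mismatched benefit would travel beyond this trial.

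**Working it through.** There is no economic figure to reproduce. The documents state no utility, willingness-to-pay threshold, incremental cost, net benefit or return on investment. The check is therefore a comparison of the text, followed by an illustration on stated assumptions.

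**Comparison of the text**

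| Element | Where | Content |
|---|---|---|
| Benefit valued | 11.0 | Preventing or averting epilepsy |
| Population | 9.2.2.1 | Diagnosed and already on medication |
| Intervention | 8.1 | Reminder to take medication |
| Economic objective | 6.3 (v) | Cost-effectiveness among people with epilepsy |
| Outcomes measured | 10.1.1, 10.1.2 | Adherence; seizure frequency, stigma, quality of life |
| Quality-of-life timing | 9.2.6, Table 1 | WHOQOL-BREF at 0, 3, 6 and 12 months |

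The first row does not fit the next three. The last two rows show that the trial collects effects that would fit. Section 11.0 does not mention the arms, the control group, the adherence outcome or WHOQOL-BREF.

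**Illustration of what depends on the missing rule**

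Let L be the quality-of-life loss due to epilepsy, s the share of L regained by a person who becomes adherent, d the absolute gain in the proportion adherent, λ the willingness to pay and C the cost per person reached. Net benefit per person reached is λ × (quality-of-life gain) − C. The gain that reminders can produce is d × s × L. Section 11.0 is compatible with three ways of applying the prevention data:

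- **A. Scaled to the trial effect:** gain d × s × L, so inflation is 1 (none).
- **B. Credited to each newly adherent person:** gain d × L, so inflation is 1/s.
- **C. Credited to each person reached:** gain L, so inflation is 1/(d × s).

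Inputs: s from 0.25 to 0.75 is an assumption, because the documents give no value. For d, section 5.1 reports an earlier Kilifi education trial with adherence rising from 36% to 85% in cases and from 38% to 74% in controls. The difference at follow-up is 85 − 74 = 11 points. Net of baseline it is (85 − 36) − (74 − 38) = 13 points. That was a different intervention, so d from 0.11 to 0.13 is only a guide.

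- Rule B: 1/0.75 = 1.3 to 1/0.25 = 4.
- Rule C: 1/(0.13 × 0.75) = 10 to 1/(0.11 × 0.25) = 36.

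With a wider s of 0.1 to 0.9, rule B gives 1/0.9 = 1.1 to 1/0.1 = 10.

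The effect on a threshold for d can be shown the same way. Setting net benefit to zero gives d = C/(λ × s × L) for the benefit reminders can produce, and d = C/(λ × L) under rule B. The rule B threshold is s times the proper one, which is 25% to 75% of it on the assumed range.

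All these ratios apply to the quality-of-life term only. Net benefit subtracts a cost, so a fold-change in that term is not the same fold-change in net benefit.

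**The case against.** The strongest reply is that section 11.0 should be read as a whole. It begins with a model of investing in management, informed by the effect of treatment measures. The averting benefit and the net-benefit step are additions to that model. Effectiveness, coverage and the costs of treated and untreated epilepsy are all adjustable inputs. Since objective (v) concerns people who have epilepsy, averting epilepsy may be loose wording for averting its burden. This is one of five secondary objectives and does not touch the primary outcome or the randomisation.

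Much of this stands. Prevention is not the only element of the economic evaluation, and the sponsor may intend to scale the benefit to the trial effect. But the net-benefit step is given its own quality-of-life source, that source is prevention, and no scaling rule is stated. If scaling is intended, the section has to say so.

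A reader might infer two stronger things. One is that the economic benefit is overstated many-fold. Only rule C reaches tens-fold on the assumptions above, the plan does not state that rule, and the analysis has not yet been done. The other is that a message type with no effect could still show a positive economic case. That also needs rule C: under A and B, d = 0 gives a gain of zero. Rule C also sits poorly with a section that treats effectiveness as an input and looks for its minimum. The threshold analysis itself is described in terms of return on investment and is not tied to the prevention data, so its bias is conditional as well.

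**Conclusion.** The point holds as a mismatch. Followed as written, the net-benefit analysis uses a benefit that the intervention cannot produce and that does not answer objective (v). This is a wrong input, not merely missing detail. The risk is of overstatement, provided that improved adherence recovers less quality of life than never having epilepsy (s below 1).

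The size cannot be computed from the documents. It runs from none under rule A, through 1.3- to 4-fold in the quality-of-life term under rule B with s from 0.25 to 0.75, to larger values only under a rule that the plan does not state. The consequence is confined to the economic objective and the model to be distributed from it.

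**What to change.** In section 11.0:

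- Replace the benefit of preventing or averting epilepsy with the trial's own 12-month differences, each reminder arm against control and by site: adherence, plus seizure frequency and WHOQOL-BREF where usable.
- Name these differences as the effect in both the net-benefit and the threshold analyses, and carry their confidence intervals through the model.
- State how they are converted to the value used in net benefit. Neither adherence nor WHOQOL-BREF is in money or utility units, and the documents give no conversion. The willingness-to-pay value and time horizon should be stated with it.
- Report any prevention scenario separately from the cost-effectiveness claim for the messages.

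No new data collection is needed for the effects, as these outcomes are already planned. The costs are a little more modelling, a conversion assumption that has to be justified, and probably a less favourable economic case.

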12.0 STATISTICS

12.1 Determination of sample size

The minimum sample size determination will be based on reducing the adherence treatment gap from the current estimates of 62% in Kilifi ((Ibinda et al., 2017a) aiming for a proportion of improvement of 40%-50%. Previous studies have shown non-adherence of >60% even among clinic attendants, especially when symptoms subside. Assuming a refusal/non-consent/attrition rate of 10% and design effect of 1.5 (assuming possibility of modest clustering), if we recruit 300 patients at each arm, i.e., total of 1200 patients, we will have 95% power to detect a 50% improvement in adherence. Therefore 1,200 PWE will be randomized into 4 arms as follows: text SMS (N=300), graphic SMS (N=300), both text and graphic SMS (N=300) and control/non-reminder SMS (N=300). An allocation ratio of 1:1:1:1 across the 4 arms will be used. Since no prevalence estimates exist for the Nairobi site, we will utilise a similar sample size for each site. This sample size determination will account for these unprecedented withdrawals by recruiting a surplus of participants, assuming a proportion of 20% loss to follow up.

Table 2. Sample size adjusted for 10% attrition at varying improvements and powers

Improvement	Power			
	80%	90%	95%	
40%	588	786	971	
45%	268	358	442	
50%	154	205	253	

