4.0 ABSTRACT

Improved outcomes for epilepsy treatment depend on a continuous supply and daily adherence to antiseizure medications (ASMs). In Kilifi County, the treatment gap which includes both the diagnostic and adherence gap, is greater than 70% and we have found interruption of supply of ASMs to peripheral clinics, distance from clinic and lack of availability of ASMs, to be barriers to adherence. In Nairobi County, factors such as environment hazards, lack of social amenities and correlates of poverty are preponderant in slums, but the prevalence of epilepsy has not been studied in such settings and consequently, the adherence gap remains unknown. Innovative mobile Health (mHealth) strategies including messages delivered by mobile phones have been used to ensure an adequate supply of drugs in health centres, and daily mobile messages have improved adherence to medication in Human Immunodeficiency Virus (HIV) programs, for example. Text messaging requires that the patient has access to a mobile phone and can understand the text message. Multimedia messaging, such as simple pictures, may improve understanding of the necessity to take medication, particularly in people who are illiterate, and we will explore this as an avenue to improve uptake.

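### Table 2 does not follow from the stated 62% adherence gap: it reproduces from an unstated 30% control adherence, with improvement, alpha and the loss rate left unsettled

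*Combined protocol and SAP*

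**What the plan says.** All the sample-size inputs are in section 12.1 of the combined protocol and SAP.

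- Basis: "reducing the adherence treatment gap from the current estimates of 62% in Kilifi", so control adherence is 100% − 62% = 38%.
- Target: "aiming for a proportion of improvement of 40%-50" per cent. The scale (relative gain, percentage points, or level reached) is not given.
- Inflation: "Assuming a refusal/non-consent/attrition rate of 10% and design effect of 1.5". Later in the same paragraph comes a second loss figure: "assuming a proportion of 20% loss to follow up".
- Claim: with 300 in each of four arms, "we will have 95% power to detect a 50% improvement in adherence".
- "Table 2. Sample size adjusted for 10% attrition at varying improvements and powers" has rows labelled 40%, 45% and 50% improvement and columns for 80%, 90% and 95% power: 588/786/971, 268/358/442 and 154/205/253.

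No significance level is stated, and no 30% adherence figure appears. Because Nairobi has no estimate, the same number is used at each site.

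**The concern.** A sample-size table should follow from the inputs given beside it. Starting from 38%, a 50% row that needs 253 per arm for 95% power is hard to place. It is too few if 50% is the level reached, and too many if the gap is halved.

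At stake is what the trial is powered for. The text sets a target range of 40% to 50%. If the control rate and the meaning of improvement are unclear, a reader cannot tell whether the lower end of that range is covered, or which pair of adherence rates the 95% refers to.

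**Working it through.** **Inputs.** From section 12.1: 38% adherence (1 − 0.62), design effect 1.5, loss 10% or 20%, 300 per arm, 1:1 pairwise. Assumed: two-sided 5%.

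**Formula.** For control rate p1, reminder rate p2 and mean rate p̄:

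n = [1.960·√(2p̄(1−p̄)) + z·√(p1(1−p1) + p2(1−p2))]² / (p2−p1)²

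with z = 0.842, 1.282 or 1.645 for 80%, 90% or 95% power. The number per arm is n × 1.5 × 1.1.

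**Step 1. Reproduce Table 2.** Example, 30% v 50% at 95% power: (1.358 + 1.116)² / 0.04 = 152.95, and × 1.65 = 252.4, rounded up to 253.

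| Rates | 80% | 90% | 95% | Printed (row) |
|---|---|---|---|---|
| 30% v 40% | 587.3 | 785.4 | 970.7 | 588/786/971 (40%) |
| 30% v 45% | 267.9 | 357.8 | 441.8 | 268/358/442 (45%) |
| 30% v 50% | 153.4 | 204.6 | 252.4 | 154/205/253 (50%) |

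All nine cells match when rounded up. With this formula and inflation fixed, and rows read as the level reached, baselines from 20% to 39.5% were tried in steps of 0.1 point. Only 30.0% matched any cell, and it matched all nine. The table title mentions attrition only, but the match also needs the design effect.

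**Step 2. Try the stated 38%.** Per arm at 95% power, × 1.5 × 1.1:

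| Meaning of improvement | 40% | 45% | 50% |
|---|---|---|---|
| Printed in Table 2 | 971 | 442 | 253 |
| Relative gain (to 53.2%, 55.1%, 57%) | 456 | 360 | 292 |
| Adherence level reached | 25,500 | 2,120 | 729 |
| Relative cut in the gap | 170 | 133 | 107 |
| Gap falls to that level | 217 | 365 | 729 |
| Percentage points added | 61 | 46 | 35 |

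No reading gives the table. A wider search over formula, alpha and inflation found nothing from 38% that came within 3% of more than three of the nine cells.

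**Step 3. One near match.** With no inflation at all, 38% v 50% gives 267.4/357.5/441.7, which rounds up to 268/358/442, the printed 45% row. The label is then wrong, the attrition adjustment named in the title is absent, and the other two rows do not fit. It is probably coincidence.

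**Step 4. Power at 300 per arm.** The effective number m is 300 × 0.9 / 1.5 = 180 at 10% loss and 300 × 0.8 / 1.5 = 160 at 20% loss.

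Power = Φ{[(p2−p1)√m − 1.960·√(2p̄(1−p̄))] / √(p1(1−p1) + p2(1−p2))}

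Example, 38% v 57%, m = 180: (2.549 − 1.384) / 0.693 = 1.68, so 95.4%.

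| Rates | 10% loss | 20% loss |
|---|---|---|
| 38% v 57% (50% relative gain) | 95.4% | 92.9% |
| 30% v 50% (Table 2's 50% row) | 97.5% | 95.8% |
| 38% v 50% (50% reached from the stated basis) | 63% | 58% |
| 38% v 53.2% (40% relative gain) | 82.8% | 78.2% |
| 30% v 40% (Table 2's 40% row) | 51.2% | 46.6% |

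For 95% power, 38% v 57% needs 292 per arm at 10% loss, and 318 (× 1.2) or 332 (÷ 0.8) at 20%. For 30% v 50% the figures are 253, and 276 or 287.

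**Step 5. Does the baseline change what 300 can detect?** At 10% loss, the detectable difference at 80% and 95% power is 14.2 and 18.4 points from 30%, and 14.7 and 18.8 points from 38%. At 20% loss it is 15.1 and 19.5, and 15.5 and 20.0. The baseline hardly matters.

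Steps 4 and 5 are pairwise, at one site and one timepoint.

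**The case against.** **Text and table may agree.** A reader might infer that the text means a relative gain from 38% while the table means a level reached, so that the two give opposite answers on the 40% target. The documents do not establish that. Improvement is never defined, and 30% v 50% with the 20% loss also stated needs 287 per arm and gives 95.8% power at 300. On that reading text and table share one meaning, and the error is confined to the 62% basis. Against it, the loss rate attached to the power calculation is 10%, where 30% v 50% gives 97.5%. Neither reading is proved.

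**The 51% is a worst case.** It compares one reminder arm with control at one site and one visit. For 30% v 40% at 10% loss, 900 v 300 at one site gives about 68%, and 600 v 600 with both sites pooled gives about 80%. The plan also analyses adherence across all visits. But section 12.1 sizes four equal arms per site, so the pairwise figure is a fair way to read Table 2.

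**A baseline below 38% has some support.** Section 12.1 itself reports non-adherence above 60% among clinic attendants, and section 5.1 gives a 79.1% gap in Kilifi by optimal drug levels. This stands as candidate support. However, the first figure is as compatible with 62% as with 70%, the second implies 20.9% adherence, and section 12.1 uses neither to state 30%.

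**Origin of the 30%.** A reader might trace it to the abstract, where "the treatment gap which includes both the diagnostic and adherence gap, is greater than 70" per cent. That is a guess. That gap includes undiagnosed people, whereas section 9.2.2.1 requires participants to be "Taking anti-seizure medications at the time of the study".

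**Alpha is assumed.** That is so. The exact nine-cell match makes two-sided 5% likely, but the plan should say it.

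**Conclusion.** The point holds as an inconsistency between a table and its stated basis. Table 2 rests on 30% control adherence, the text gives 38%, and no tested reading of improvement from 38% produces the table. The 95% power sentence is true for 38% v 57% at 10% loss but not at 20%. It is true for 30% v 50% at either loss rate, and false for 38% v 50%. Whether the 40% end of the target is covered depends on the reading: at 10% loss, 51% power for 30% v 40% against 83% for 38% v 53.2%.

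A reader might infer that the trial is too small. The documents do not support that: 300 per arm detects nearly the same difference from either baseline. Text and table may use improvement differently, but that cannot be shown from the plan. The fault should be fixed, because readers will rely on the table. It rests on two-sided 5% and the pooled two-proportion formula.

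**What to change.** State the control rate, the reminder rate, alpha and a single loss rate, and use them in both the power sentence and Table 2. There are two ways.

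**Option 1: recompute from 38%**, with rows labelled by both rates.

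| Rates | 80/90/95% power, × 1.5 × 1.1 | Same, × 1.5 × 1.2 |
|---|---|---|
| 38% v 53.2% | 277/369/456 | 302/403/497 |
| 38% v 55.1% | 219/292/360 | 239/319/393 |
| 38% v 57% | 177/237/292 | 194/258/318 |

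The power sentence could read: with 38% control adherence, two-sided 5%, design effect 1.5 and 10% loss, 300 per arm gives 95% power for 57% adherence in one reminder arm against control at one site. If 20% loss is kept, restate that power as about 93%. Cost: the 50% row rises from 154/205/253 to 177/237/292, and the stated power may fall slightly.

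**Option 2: keep Table 2**, replace the 62% basis with a stated 30% baseline justified for people already on medication, and relabel the rows 30% v 40%, 30% v 45% and 30% v 50%. The power sentence must then name 30% v 50%, because a 50% relative gain from 30% is 45%, and that row needs 442 per arm for 95% power. Cost: a justification that section 12.1 does not now contain.

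Either way the change is wording and one table, with no extra patients.
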